8.4 Subsequent Icatibant-treated Attacks (Pubertal/Postpubertal Subjects Only)

Pubertal/postpubertal subjects may receive treatment for up to 2 subsequent HAE attacks, contingent upon having received an initial icatibant treatment and presenting with a subsequent acute attack of at least 3 days after prior treatment (see Section 4.1.3).

For subsequent attacks, study drug may be administered by study site personnel at the hospital/study center or by qualified home healthcare personnel at the subject's home. Alternatively, a parent/legal guardian/caregiver will be allowed to administer or the subject (under the supervision of a parent/legal guardian/caregiver) will be allowed to self-administer the investigational product after having received appropriate training. For all subsequent laryngeal attacks, subjects should be advised to seek medical attention in an appropriate healthcare facility immediately following treatment with icatibant.

8.4.1 Subsequent Icatibant-treated Attack Baseline Assessments

All evaluations and sample collections must be performed at the hospital/study center within 6 months prior to treatment:

- Confirm inclusion/exclusion criteria
- Menstrual cycle history (in pubertal/postpubertal females only)
- Documentation of HAE attack(s) not treated with icatibant
- Physical examination
- Vital signs
- Height and weight
- Clinical laboratory tests (serum chemistry and hematology)
- Urine pregnancy test (in females of childbearing potential)
- Reproductive hormone assessments
- Immunogenicity evaluation
- Recording of concomitant medications
- Assessment of AEs
- Training for parent/legal guardian/caregiver on how to assess HAE symptoms using the 5-point rating scale, time to initial symptom relief, and injection site reactions (for subjects who have expressed interest in self-administering or having a parent/legal guardian/caregiver administer icatibant in the home)
- Training on icatibant administration (for subjects who have expressed interest in self-administration or having a parent/legal guardian/caregiver administer icatibant in the home)
- Dispense 1 syringe of study drug (for subjects who have expressed interest in being treated at home by a home healthcare provider, parent/legal guardian/caregiver, or self-administration)
- Instruct the subject (parent/legal guardian/caregiver) to record a weight measurement every month and to contact the hospital/study center to confirm dosing (for subjects who have expressed interest in being treated at home by a home healthcare provider, parent/legal guardian/caregiver, or self-administration)

- Instruct the subject (parent/legal guardian/caregiver) to contact the hospital/study center (or their home healthcare professional in the event the investigator is not available) at the time of a subsequent attack to confirm the HAE attack diagnosis.

8.4.2 Treatment Period (Day 1 to Day 8 [± 1 Day])

8.4.2.1 Day of Subsequent Attack (Day 1)

When a pubertal/postpubertal subject experiences an acute HAE attack, subjects (parent/legal guardian/caregiver) will contact the hospital/study center (or their home healthcare professional in the event the investigator is not available) to confirm the HAE attack diagnosis.

The investigator (or the home healthcare professional in the event the investigator is not available), in consultation with the subject's preference, will determine whether the subject will be treated at the hospital/study center, at home by a qualified home healthcare personnel, at home by the trained parent/legal guardian/caregiver, or by self-administration. The qualified home healthcare person will be contacted, if applicable.

The following will occur prior to study drug administration:

	Subject Treated at Study Site	Subject Treated at Home
Call hospital/study center (or their home healthcare professional in the event the investigator is not available) to confirm the HAE attack diagnosis	X	X
Investigator Symptom Score	X	
Home Healthcare Provide or Parent/Legal Guardian/Caregiver Symptom Score	X	X
Subject Self-Assessment of Pain	X	X
Urine pregnancy test	X	X
Concomitant Medications	X	X
Adverse Events	X	X

- Assessment of HAE symptoms
 - The investigator will assess HAE symptoms using the Investigator Symptom Score if the subject is treated at the hospital/study center
 - The home healthcare provider will assess HAE symptoms using the Home Healthcare Provider or Parent/Legal Guardian/Caregiver Symptom Score if the subject is treated at home
 - The parent/legal guardian/caregiver will assess HAE symptoms using the Home Healthcare Provider or Parent/Legal Guardian/Caregiver Symptom Score if the subject is treated at either the hospital/study site or at home
- Subject will self-assess HAE-related pain using diary FPS-R
- Urine pregnancy test for females of child-bearing potential
- Concomitant medications will be recorded
- Adverse events will be recorded

Once the pretreatment assessments are completed, icatibant will be administered (Day 1, Time 0).

- Study drug may be administered by study site personnel at the hospital/study center or by qualified home healthcare personnel at the subject's home. Alternatively, a parent/legal guardian/caregiver will be allowed to administer or the subject (under the supervision of a parent/legal guardian/caregiver) will be allowed to self-administer the investigational product after having received appropriate training.
- For all subsequent laryngeal attacks, subjects should be advised to seek medical attention in an appropriate healthcare facility immediately following treatment with icatibant.

The subject will be observed by the investigator, the home healthcare provider or the parent/guardian/caregiver for a minimum of 2 hours after icatibant administration.

The following will occur after icatibant administration:

	Subject Treated at Study Site	Subject Treated at Home
Icatibant Administration	X	X
Investigator Symptom Score	X	
Home Healthcare Provide or Parent/Legal Guardian/Caregiver Symptom Score	X	X
Subject Self-Assessment of Pain	X	X
Injection site reaction evaluation	X	X
Concomitant Medications	X	X
Adverse Events	X	X
Contact site 6 to 8 hours after attack	X	X

- HAE symptoms will be assessed at Day 1, 1 hour [± 10 minutes] post dose and 2 hours [± 10 minutes] post dose AND every 2 hours [± 10 minutes] until the subject's symptoms are absent or mild [if the subject's symptoms are not absent or mild at 2 hours post dose]
 - The investigator will assess HAE symptoms using the Investigator Symptom Score and record the time of initial symptom relief if the subject is treated at the hospital/study center
 - The home healthcare provider will assess HAE symptoms using the Home Healthcare Provider or Parent/Legal Guardian/Caregiver Symptom Score and record the time of initial symptom relief if the subject is treated at home
 - The parent/legal guardian/caregiver will assess HAE symptoms using the Home Healthcare Provider or Parent/Legal Guardian/Caregiver Symptom Score if the subject is treated at either the hospital/study site or at home
- The subject will self-assess pain using diary FPS-R (1 hour [± 10 minutes] post dose and 2 hours [± 10 minutes] post dose, and every 2 hours [± 10 minutes] until pain is absent [if the subject's pain is not absent at 2 hours post dose]);

- Injection site reaction will be recorded (1 hour [± 10 minutes] post dose and 2 [± 0.5] hours post dose, and every 2 [± 0.5] hours until injection site reaction is mild or absent [if the subject's injection site reaction is not mild or absent at 2 hours post dose]);
- Concomitant medications will be recorded
- Adverse events will be recorded
- Subjects (parent/legal guardian/caregiver) will contact the hospital/study center 6 to 8 hours after icatibant administration to update the investigator of the subject's condition

8.4.2.2 Day 2 (24 [± 4] hours)

On Day 2 (24 [± 4] hours):

- The subject will self-assess HAE pain using diary FPS-R
- Injection site reaction will be recorded
- Concomitant medications will be recorded
- Adverse events will be recorded

8.4.3 Follow-up Visits

Each treatment for a subsequent attack will require a Day 8 and a Day 90 follow up visit. If a subsequent attack occurs within 3 days of the Day 8 follow-up visit for the previous attack, the visits for Day 1 (of the subsequent icatibant-treated attack) and Day 8 (of the prior icatibant-treated attack) will be combined. If a subsequent attack occurs within 7 days of the Day 90 follow-up visit for the previous attack, the visits for Day 8 (of the subsequent icatibant-treated attack) and Day 90 (of the prior icatibant-treated attack) will be combined.

8.4.3.1 Day 8 (± 1 day)

The subject will return to the hospital/study on Day 8 (± 1 day). The following evaluations and sample collections will be performed on Day 8:

- Vital signs
- Reproductive hormone assessments
- Immunogenicity evaluation
- Injection site reaction evaluation
- Concomitant medications will be recorded
- Adverse events will be recorded

8.4.3.2 Day 90 (± 7 days)

- Physical examination
- Vital signs
- Height and weight
- Clinical laboratory tests (serum chemistry, hematology)
- Urine pregnancy test (in females of childbearing potential)
- Reproductive hormone assessments
- Immunogenicity evaluation
- Menstrual cycle history (in pubertal/postpubertal females)

- Recording of concomitant medications
- Assessment of AEs
- Documentation of HAE attack(s) not treated with icatibant

9 QUALITY CONTROL AND ASSURANCE

Training will occur at an investigator meeting or at the site initiation visit or both, and instruction manuals will be provided to aid consistency in data collection and reporting across sites.

Clinical sites will be monitored by the sponsor or its designee to ensure the accuracy of data against source documents.

The required data will be captured in a validated clinical data management system that is compliant with the Food and Drug Administration (FDA) 21 Code of Federal Regulations (CFR) Part 11 Guidance. The clinical trial database will include an audit trail to document any evidence of data processing or activity on each data field by each user. Users will be trained and given restricted access, based on their role(s) in the study, through a password-protected environment.

Data entered in the system will be reviewed manually for validity and completeness against the source documents by a clinical monitor from the sponsor or its designee. If necessary, the study site will be contacted for corrections or clarifications; all missing data will be accounted for.

Serious adverse event information captured in the clinical trial database will be reconciled with the information captured in the Pharmacovigilance database.

10 PLANNED STATISTICAL METHODS

10.1 General Considerations

All statistical analyses will be performed using Statistical Analysis System® (SAS) statistical software (SAS Institute, North Carolina, USA) except for the population PK modeling which will be performed with nonlinear mixed effect modeling software (eg, Phoenix NLME module, Pharsight Corp.). A separate analytic plan will be developed to support the analysis of PK data. The analysis methods for all other study data (disposition, demographic and pretreatment characteristics, efficacy variables, and safety variables) will be detailed in the statistical analysis plan (SAP). Data will be summarized with respect to disposition, demographic, pretreatment characteristics, PK variables, safety variables, and efficacy variables. Summary statistics for continuous variables will include the number of subjects, the mean, median, standard deviation, and range. For PK parameters, the coefficient of variation and geometric mean also will be provided. For categorical data, summaries will include counts and percentages. For time to event data, the median time to event and other summary statistics will be estimated using the method of Kaplan and Meier.

10.2 Determination of Sample Size

The study will enroll a sufficient number of children and adolescents to ensure study completion of 30 subjects. The study population is planned to consist of at least 10 prepubertal and 20 pubertal/postpubertal subjects from 2 to less than 18 years of age. Though empirically derived and not based on a formal sample size calculation, this sample size will provide basic information concerning the PK, tolerability and safety, and efficacy of icatibant in children and adolescents with HAE.

10.3 Analysis Populations

The following populations will be used in the analysis:

The Efficacy Population will consist of those subjects who were treated with icatibant for their first and any additional attacks.

The PK Population will consist of those subjects who were treated with icatibant and had sufficient icatibant plasma concentration time measurements to derive primary PK parameters.

The Safety Population will consist of those subjects who were treated with icatibant at least once.

All efficacy analyses will be performed on the Efficacy Population. The corresponding tabular summaries and listings will be presented by the subject stratification group at enrollment (ie, prepubertal group or pubertal/postpubertal group) and icatibant-treated attack number.

The PK analyses will be based on the PK Population.

Safety and tolerability analyses will be based on the Safety Population. All tabular summaries and listings within this population will be presented by the subject stratification group and icatibant exposure number.

10.4 Demographics and Baseline Characteristics

Demographic data and pretreatment characteristics will be summarized separately for the Safety Population and the Efficacy Population.

10.5 Pharmacokinetic Analysis

A primary objective of the study is to investigate the PK of a single SC injection of icatibant in pediatric subjects. All PK analyses will use the PK population.

Plasma concentrations of icatibant and metabolites (ie, M1 and M2) and actual blood sampling times will be listed by subject and sampling time. Plasma concentrations will be summarized using descriptive statistics (number, mean and standard deviation). Pharmacokinetic parameters for icatibant and metabolites will be listed by subject and will be summarized using descriptive statistics (number, mean, standard deviation, coefficient of variation, geometric mean, minimum, median, maximum). Individual and mean plasma concentrations of icatibant and metabolites versus time will be displayed on linear and semi-logarithmic axes.

10.5.1 Estimation of PK Parameters

10.5.1.1 Noncompartmental Modeling

For subjects in whom the number of samples is sufficient to permit noncompartmental modeling, individual and mean PK parameters will be computed for icatibant and metabolites (M1 and M2) using standard noncompartmental methods, where possible, using the WinNonLin software package (Pharsight Corp., Mountain View, CA). For descriptive statistical tabulation of mean plasma concentrations and graphical displays, nominal collection times will be used, while all PK analysis and parameter calculations will use actual collection times. Plasma concentrations <limit of quantification (LOQ) will be treated as 0 for the calculation of the descriptive statistics for plasma concentrations at each sampling time. For the pharmacokinetic analysis, plasma concentrations <LOQ that occurred from predose to the first concentration \geq LOQ will be treated as 0 and those that occur thereafter will be treated as missing.

Pharmacokinetic parameter estimates will include, where appropriate: icatibant and metabolite concentrations at each sampling time, T_{max} , actual peak (C_{max}) and minimum (C_{min}) concentrations, CL/F, AUC_{0-last} and AUC_{0-inf} , MRT, volume of distribution at steady state (V_{ss}/F) and $t_{1/2}$.

The distribution of continuous data will be evaluated using parametric tests. A transformation, such as logs, will be used where appropriate. Multiple regression analysis, with an appropriate transformation on the dependent variable, will be used to assess the contribution of potential PK covariates while controlling for demographic covariates (eg, subject's age and gender) to the inter-subject variability of icatibant PK parameters. The multivariable analysis will be considered the primary statistical analysis. A p-value of 0.05 will be considered statistically significant for all analyses.

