7.10 Pharmacokinetic Assessments

7.10.1 Pharmacokinetic Variables

Individual patient PK variables for icatibant and major metabolites will be determined from the respective plasma concentration time profiles where appropriate, using noncompartmental methods.

A population PK model will be derived to evaluate the correlation of key covariates (ie, age, body weight, gender) on the PK profile of icatibant.

Pharmacokinetic variables will be determined by full sampling and noncompartmental methods where possible, and elsewhere by sparse sampling (at least 4 to 7 time points) and a population PK approach using nonlinear mixed effects modeling software.

Primary and secondary pharmacokinetic parameter estimates will be reported and include time to peak concentration (T_{max}), actual peak (C_{max}) and minimum (C_{min}) concentrations, total body clearance (CL/F), actual AUC_{0-last} and AUC_{0-inf} , mean residence time (MRT), volume of distribution at steady state (V_{ss}/F) and terminal elimination half-life ($t_{1/2}$).

The methods to be used for estimation of PK parameter values are described in Section 10.5.1.

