10.5.1.2 Compartmental Modeling Using Population Methods

Nonlinear mixed effects modeling will be used to define individual subject profiles and if possible, parameter estimates. The structural PK model will be developed and validated using PK information obtained from adult subjects and will enable delineation of the impact of age-dependent changes on icatibant disposition. Development of this model will allow for characterization and better prediction of the dose-concentration-exposure relationship for icatibant in pediatric subjects. Population PK modeling will be performed with nonlinear mixed effect modeling software (eg, NONMEM, Globomax LLC or WinNonMix, Pharsight Corp.). The program will estimate the inter- and intra-individual variability of PK parameter estimates. Both weight-normalization and allometric scaling principles will be evaluated. For selecting preliminary meaningful covariates the general additive model (GAM) analysis will be used. Variables to be considered will include (but are not limited to): age, sex, ethnicity, total and lean bodyweight (TBW, LBW), body mass index (BMI), and body surface area (BSA).

Monte Carlo simulation experiments based on the model(s) developed above may be performed by a validated simulation software program (eg, Trial Simulator, Pharsight Corp.) to assess the response patterns for various dosage regimens of icatibant treatments in the pediatric population.

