10.9 Data Monitoring and Interim Analysis

A DSMB will be set up to review the safety, tolerability, PK, and efficacy data on an ongoing basis. The DSMB is described in Section 11.8; its goal will be to assess the risk/benefit of icatibant treatment in this pediatric population.

An analysis of the data for DSMB review is planned after the first 4 subjects in the pubertal/postpubertal group have been treated, and will be repeated at subsequent time points as specified in the DSMB charter. Because no formal hypothesis testing is planned, multiplicity concerns regarding repeated analyses are not an issue.

Based on the anticipated sequence of data being generated in the study, an initial interim analysis of the data from the initial attack (N=30) is planned. It is expected that this will be followed by a final analysis to include the data of patients treated for subsequent attacks. This sequence is based on the anticipated sequence of data being generated during the study and may be modified to fit the actual study conduct.

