## **9. STATISTICAL/ANALYTIC ISSUES**

### **9.1 Adjustment for Covariates**

Given the small number of subjects treated in the study, no modelling approach will be performed to analyze the study data. Therefore, adjustment for covariates is not necessary.

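### The protocol makes an unspecified PK covariate regression its primary statistical analysis at an unadjusted 0.05, which contradicts its own statement that no formal testing is planned

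*Protocol*

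**What the plan says.** Protocol 10.5.1.1 plans a multiple regression to assess what potential covariates contribute "to the inter-subject variability of icatibant PK parameters". Age and gender appear there only as examples of demographic terms to adjust for. The section continues: "The multivariable analysis will be considered the primary statistical analysis". It then sets the decision rule: "A p-value of 0.05 will be considered statistically significant for all analyses".

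The same section lists nine parameters: CL/F, AUC0-last, AUC0-inf, Cmax, Cmin, Tmax, t1/2, MRT and Vss/F. It does not say which of them are regressed, which covariates are tested, or how several tests are handled together. Protocol 3.1 makes the PK profile a primary endpoint. Protocol 10.2 plans 30 subjects without a formal sample size calculation.

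Protocol 10.9 says: "Because no formal hypothesis testing is planned, multiplicity concerns regarding repeated analyses are not an issue". SAP 9.3 repeats this in the past tense.

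**The concern.** A fixed 0.05 threshold on an analysis labelled primary is a testing rule. Section 10.9 concerns repeated looks by the DSMB and at the interim analysis, but its premise, that nothing is formally tested, is stated for the study as a whole. Both passages cannot stand as written.

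At stake is how the PK results are reported. With no main parameter and no adjustment, any term that crosses 0.05 in any of the regressions could be reported as a significant age, sex or size effect from the primary analysis. With about 30 subjects and no power calculation, the threshold can also mislead the other way: a non-significant term could be read as showing no effect.

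**Working it through.** The documents state no number of tests and no familywise error, so there is no planned figure to reproduce. The check asks how large the risk could be.

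**Inputs from the documents.** Per-test level 0.05 and nine icatibant parameters (Protocol 10.5.1.1); about 30 subjects (10.2).

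**Assumed number of covariates.** No list is given for this regression, so a range is used:
- 1: body weight, if age and gender are adjusters only.
- 3: age, body weight and gender, borrowed from the population-model text in Protocol 7.10.1.
- 5: the seven below without age and sex, which are then adjusters.
- 7: age, sex, ethnicity, total weight, lean weight, BMI and BSA, borrowed from the open-ended population-model list in Protocol 10.5.1.2.

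**Formulas for m tests with no true effects.** Expected false positives = 0.05 × m. Chance of at least one, if independent = 1 − 0.95^m. The second is used as a ceiling.

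- m = 9 × 1 = 9: 0.45 expected; 1 − 0.95^9 = 37%
- m = 9 × 3 = 27: 1.35 expected; 1 − 0.95^27 = 75%
- m = 9 × 5 = 45: 2.25 expected; 1 − 0.95^45 = 90%
- m = 9 × 7 = 63: 3.15 expected; 1 − 0.95^63 = 96%

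Reaching 95% takes 59 independent tests (ln 0.05 / ln 0.95 = 58.4, rounded up).

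**Allowing for correlation.** The tests are far from independent. For a given dose, CL/F and AUC0-inf determine each other; MRT tracks t1/2; total weight, lean weight and BSA move together. A simulation of 4,000 null trials took this into account. It used:
- a one-compartment SC model at a fixed 30 mg dose, sampled at the pubertal times of Protocol 7.10.2;
- log-transformed parameters and two-sided t-tests at 0.05;
- adult variability from Protocol 1.2.1: clearance CV 58/245 = 24%, volume CV 8.7/29.0 = 30%;
- assumed values of 40% CV for the absorption rate, 10% assay error, and correlations of about 0.87 to 0.99 among age, total weight, lean weight and BSA.

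| Model | Tests | Chance of at least one, n = 30 | n = 20 | Mean false positives, n = 30 |
|---|---|---|---|---|
| 3 covariates, joint | 27 | 40% | 39% | 1.40 |
| 5 covariates, each adjusted for age and sex | 45 | 48% | 47% | 2.29 |
| 7 covariates, one at a time | 63 | 60% | 59% | 3.12 |
| 7 covariates, joint | 63 | 66% | 65% | 3.15 |

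The mean counts agree with 0.05 × m, as they should. Correlation leaves the average number of false positives unchanged but concentrates them in fewer trials. The 9-test case was not simulated; only its ceiling of 37% is available.

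**The case against.** **The PK plan is a separate document.** Protocol 10.1 and SAP 2.1 and 7.1 defer PK to a plan that was not available. It may name the parameters, the covariates and a multiplicity rule. This stands: one cannot say that the trial has no error control for PK, only that the protocol states none. The PK plan would not by itself remove the primary label and the 0.05 rule from the protocol.

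**The conflict is narrow.** Section 10.9 speaks of formal testing and repeated analyses, and the 0.05 sentence sits in a PK subsection of a study that is otherwise descriptive. A reader might infer that 0.05 governs safety and efficacy too, but the SAP sets no such threshold. The clash is between two protocol passages, and it remains.

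**Stronger readings that the documents do not support:**
- A reader might count tests on the two metabolites as well. Section 10.5.1.1 confines the regression to icatibant parameters.
- A reader might take the 96% figure to mean that false findings are near certain. It assumes independence and borrows seven covariates from a different analysis. It also assumes no real effects, and a true effect of body size on CL/F would not be a false finding.
- A reader might cite SAP 9.1, where "no modelling approach will be performed to analyze the study data", as a second contradiction. That SAP covers safety and efficacy only, so it does not conflict with a PK regression.
- A reader might suppose that these p-values drive the dosing simulations. Protocol 10.5.1.2 bases the simulations on the population models, which have their own covariate screen.

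**Conclusion.** The contradiction between Protocol 10.5.1.1 and 10.9 is real and concerns a primary endpoint. As the protocol stands, a primary PK regression with up to nine outcomes, unnamed covariates and no multiplicity rule is tested at an unadjusted 0.05.

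The size of the risk is conditional on assumptions. For 27 to 63 tests it is about 40% to 66% once correlation is allowed for, or 8 to 13 times the nominal 5% (40/5 = 8; 66/5 = 13.2). This rests on borrowed covariate lists, adult variability, a fixed dose, the fuller pubertal sampling schedule for every subject, and no true effects. A PK plan that fixes one parameter and a few covariates would bring the risk down sharply: one parameter with three covariates has a ceiling of 1 − 0.95^3 = 14%.

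**What to change.** **Preferred.** In Protocol 10.5.1.1, delete the 0.05 sentence and the primary statistical analysis label. Report covariate effects as exploratory estimates with 95% confidence intervals. Reword the remark about checking distributions with parametric tests, so that 10.5.1.1 and 10.9 agree.

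**Alternative.** Keep testing, but name the PK parameter or parameters and the covariates, state a multiplicity rule, and amend 10.9 to say that PK covariates are tested. Bonferroni thresholds would be 0.05/27 = 0.00185 or 0.05/63 = 0.00079 for the wider sets, so a short list is needed to leave a usable test. Which parameter leads is the sponsor's choice. Protocol 1.2.2 reports the initial-treatment part as complete, and PK is sampled only there (7.10.2). Naming parameters now would therefore count as prespecification only if the PK plan had done so beforehand.

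**Cost.** Protocol and PK-plan wording, with no new data and no change in conduct. Under the preferred option, covariates can no longer be called significant.
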